#### 5.4.2 Subgroup analysis

Exploratory subgroup analyses aim at identifying subgroups which may especially benefit or do not respond well to the treatment groups offered, as measured by the reduction in gastrointestinal symptom severity (IBS-SSS). For this purpose, an ANCOVA for the IBS-SSS at 3 months as dependent variable will be performed in the ITT population, adjusted for the IBS-SSS at baseline and including group allocation as factor and the interaction between group and specified interaction variable. For each defined interaction variable, a separate ANCOVA model will be examined.

Interaction test p-values and. Subgroup-specific means and pairwise effect differences with 95% confidence intervals will be reported in the case of interaction tests with p values of less than 0.15 in accordance with the EMA guideline on the investigation of subgroups in confirmatory clinical trials. The presented p-values will not be adjusted for multiple comparisons.

The following subgroup variables will be investigated in separate ANCOVA models regarding their potential interaction with the intervention groups with respect to the change in the IBS-SSS from baseline to 3 months:

*Key subgroups*

- Diagnosis (UC vs. IBS)
- Gender (female vs. male; diverse patients are excluded for this analysis)

*Exploratory subgroups*

- Age (young [ $\leq$ first tercile] vs. middle aged vs. old [ $>$ third tercile])
- Migration background (none vs. 2nd generation [mother and/or father not born in Germany] vs. 1st generation [patient not born in Germany])
- Education ( $\leq$  10 years in school vs.  $>$  10 years in school)
- Duration of symptoms in years ( $<$ 5 years vs 5-10 years vs  $>$ 10 years)
- Baseline IBS-SSS none [0-74] vs mild [ $\geq$ 75-174] vs moderate [ $\geq$ 175 - 300] vs severe [ $>$ 300] ( this analysis will not be adjusted for baseline IBS-SSS)
- Somatic symptom severity (PHQ-15 categorical:  $<$ 10 vs  $\geq$ 10)
- Somatosensory Amplification (SSAS split at median ( $\leq$ 15 vs  $>$  15))
- PHQ-15 categorical:  $<$ 10 vs  $\geq$ 10)
- GAD-7 categorical:  $<$ 10 vs  $\geq$ 10
- TAS-20 as 20-60 vs  $\geq$  61
- ERQ suppression split at median ( $\leq$ 3.25 vs  $>$  3.25)
- SSD-12  $<$  24 vs  $\geq$  24
- Adverse childhood events (ACE-D: 0 vs. 1-3 vs.  $\geq$  4)
- BMI ( $<$  18,5 vs.  $\geq$  18,5 to 24,9 vs.  $\geq$  25)
- Systemic inflammation (CRP: normal range [under detection limit and normal range up to  $<$  5mg/l] vs. abnormal  $\geq$  5mg/l])
- Number of somatic comorbidities (0-1 vs. 2-3 vs.  $\geq$  4)
- for UC only:
  - Disease activity (: SCCAI 0-4 vs.  $\geq$  5)
  - Gastrointestinal inflammation (fecal calprotectin: normal range [under detection limit and normal range up to  $<$  50 $\mu$ g/g] vs. abnormal  $\geq$  50  $\mu$ g/g )

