## 2.3 Sample size

This trial is powered with regard to the difference between intervention 1 (GUT.EXPECT+SC) versus the control condition (SC). Based on the literature reviewed, we assume a within-group standard deviation (SD) of 75 points on the irritable bowel syndrome severity scoring system (IBS-SSS). Given this SD, a difference of 40 points on the IBS-SSS can be detected with a power of 80%, using a two-sided alpha of 5%, by including 29 patients per group, yielding a total sample size of n=87 for UC and IBS, respectively. Based on the results of our prospective cohort study, we assume a loss to follow-up between baseline and the primary outcome measurement (ie, 3 months follow-up) of 25%, resulting in a total of n=117 randomised patients for UC and IBS, respectively. Assuming that 50% of patients with UC or IBS will meet the inclusion criteria, n=234 patients per diagnostic group will be assessed for eligibility.

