### 3.3.3 Per Protocol population (PP)

The Per Protocol population includes all patients randomized who have no major protocol violation and for whom data is available from the follow-up measurement point.

Major protocol violations are any unapproved changes in the research study design and/or procedures that are within the investigator's control and not in accordance with

the IEC/IRB -approved protocol that may affect the participant’s rights, safety or well-being, or the completeness, accuracy and reliability of the study data.

Major protocol violation includes ineligible participants who were included in the trial by mistake, and those for whom the intervention or other procedure differed from that outlined in the protocol, or failure of consent process. Major protocol violations can occur at different times of the study and are defined in Table 1

Table 1: Major protocol violations at different times of study

Upon Inclusion:	
 
• IBS-SSS < 175 in the inclusion screening
 
• IBS-SSS < 75 in the baseline assessment (may differ from the inclusion screening)
 
• ROME IV criteria not fully met (IBS)
 
• No validated diagnosis of UC or IBS (doctor's letter or UKE/IK-confirmation)
 
• No guideline-appropriate treatment
 
• Missing or incomplete study consent
 
• Acute suicidality
 
• Acute illness requiring treatment (except UC/IBS)
 
• Psychotherapy in the last 3 months or currently starting psychotherapy
 
• Insufficient German language skills
 
• Significant cognitive deficits
 

At Baseline:	
 
• Unreported SAE
 

At 6-week follow-up:	
 
• 6-week follow-up completed before the 3rd intervention session (GUT.EXPECT, GUT.SUPPORT)
 

At 3-month follow-up:	
 
• More than 2 missing intervention sessions (GUT.EXPECT, GUT.SUPPORT)
 
• Data collection takes place before the booster session (GUT.EXPECT, GUT.SUPPORT)
 

At 12-month follow-up:	
 
• For IBS: missing telephone SKID interview, as the ROME IV criteria were not collected without it
 

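### SAP 5.4.2: the exploratory baseline-severity subgroup model drops the continuous baseline IBS-SSS, which costs a little precision and ties the result to the choice between 3-month score and change score

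*SAP*

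**What the plan says.** SAP 5.4.2 sets out exploratory subgroup analyses in the ITT population. Each uses an ANCOVA with the 3-month IBS-SSS as dependent variable, baseline IBS-SSS as covariate, treatment group as factor, and a group-by-subgroup interaction. Subgroup means and pairwise differences with 95% intervals follow if the interaction p-value is below 0.15. Later, the same section describes the question as one about the change in IBS-SSS from baseline to 3 months.

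One entry in the exploratory list is baseline severity, in four classes: 0–74, 75–174, 175–300 and above 300. It begins "Baseline IBS-SSS none [0-74] vs mild" and adds that "this analysis will not be adjusted for baseline IBS-SSS". No reason is given.

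Table 1 in SAP 3.3.3 lists two IBS-SSS entries among major violations upon inclusion: a score below 175 at screening, and a score below "75 in the baseline assessment (may differ from the inclusion screening". The second range is the same as the lowest subgroup class.

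**The concern.** Grouping a continuous score does not use it up. Patients within a class 100 or 200 points wide still differ in baseline severity, and that difference still predicts the 3-month score. Without the covariate, this variation goes into the residual and chance imbalance between arms within a class is not corrected.

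There is also a definitional consequence. With baseline as a covariate, modelling the 3-month score or the change gives the same treatment contrasts. Without it, the two give different contrasts, and 5.4.2 names both.

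The secondary matter is the lowest class. Patients enter through a screening floor of 175, and a baseline score below 75 is itself a violation, so the class should be almost empty. The SAP still promises means and pairwise differences for it if p<0.15, with no minimum cell size and no merging rule. At stake is how clearly and precisely one exploratory question is answered: whether benefit depends on initial severity.

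**Working it through.** **Inputs from the SAP.** In 2.3: "we assume a within-group standard deviation (SD) of 75 points"; a 40-point difference, 80% power, two-sided 5%; "by including 29 patients per group, yielding a total sample size of n=87 for UC and IBS, respectively"; 25% loss to follow-up; 117 randomised per disease. From 5.4.2: the classes and the 0.15 threshold.

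**The plan's own figure.** The SAP gives no figure for this subgroup test. Its sample size supplies the numbers analysed. For two means, n per arm = 2(1.960 + 0.842)² × 75² / 40² ≈ 55.2, so 56. The stated 29 per arm per disease makes 58 per arm when the diseases are pooled, with power 0.82. Allowing for dropout, 29/0.75 = 38.7, so 39 per arm, and 3 × 39 = 117. Evaluable total: 2 × 87 = 174.

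**Assumptions, not in the SAP.** Screening and baseline scores are bivariate normal, then restricted to screening ≥175. One set uses mean 200–275, SD 75 and screening–baseline correlation 0.5–0.85. A second uses mean 240–280, SD 75–90 and correlation 0.6–0.8.

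**Step 1: what the classes retain.** The share of baseline variance explained by the four classes (R²) is 0.71–0.79 in the first set and 0.72–0.80 in the second.

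**Step 2: cost of dropping the score.** With baseline–outcome correlation ρ, the residual variance ratio is (1 − ρ²R²)/(1 − ρ²).
- ρ = 0.4, R² = 0.80: 0.872/0.840 = 1.04; square root 1.02.
- ρ = 0.6, R² = 0.72: 0.741/0.640 = 1.16; square root 1.08.

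So variance rises by 4–16% and interval width by 2–8%. For a wider range of ρ (first set), standard errors rise by 1.0–1.4% at 0.3, 3.4–4.8% at 0.5 and 9.5–13.3% at 0.7.

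**Step 3: interaction power at p<0.15.** Simulation with 1,500 runs, 174 evaluable patients, mean 250, SD 75, screening–baseline correlation 0.7, and arm effects of 0/0/40/80 points across the four classes:

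| ρ | As planned | Four classes + score | Three classes + score |
|---|---|---|---|
| 0.3 | 0.49 | 0.50 | 0.50 |
| 0.5 | 0.56 | 0.58 | 0.59 |
| 0.7 | 0.67 | 0.74 | 0.74 |

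Each entry has a Monte Carlo standard error of about √(0.25/1500) = 0.013, so the 1-point gain at ρ = 0.3 means little or none. A second simulation (3,000 runs, 176 completers, ρ = 0.5, GUT.EXPECT effect only above 300) gave 0.44 as planned and 0.48 with three classes plus the score for a 40-point effect, 0.71 and 0.73 for 60 points, and 0.15 and 0.16 with no effect. The gain comes almost wholly from the covariate.

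**Step 4: 3-month score or change.** Without the covariate, the two contrasts within a class differ by exactly the difference in mean baseline between the arms in that class. As an illustration, take the 175–300 class with scores spread evenly: SD = 125/√12 ≈ 36. At mean 250 and screening–baseline correlation 0.7, about 62% of 58 patients per arm, or 36, fall there. The gap between the two answers then has a standard deviation of 36 × √(2/36) ≈ 8.5 points. With the covariate the gap is zero.

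**Step 5: the lowest class.** In the first set its share is at most 1.62%: 234 × 0.0162 = 3.8 patients randomised, 174 × 0.0162 = 2.8 evaluable; at the other end the count is essentially zero. The second set gives 0 to 2 of 234. With share p, the chance that at least one arm has no evaluable patient in the class is 1 − [1 − (1 − p)^58]³, which runs from 0.77 to about 1.00.

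**The case against.** The strongest defence is that little is lost. The classes are in the model and carry most of the baseline information, randomisation keeps the comparison unbiased, and not entering one variable both as categories and as a score is an openly pre-specified choice. The analysis is exploratory, with unadjusted p-values. All of that stands and limits the weight of the point. It does not give a reason to leave the score out: with R² of 0.71–0.80 the score is not aliased with the classes, and the trial already collects it.

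Two stronger readings are tempting, and the document supports neither.

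- A reader might infer that the nearly empty class wastes 2 of the 6 nominal interaction degrees of freedom, (4 − 1)(3 − 1). A class with evaluable patients in k arms adds only k − 1, so spending 2 needs patients in all three arms. With 0, 1 or 2 patients it adds at most 0, 0 or 1. In the first simulation the test had 4 degrees of freedom in about 97% of runs. The 4–6 point power loss that arises if all 6 are spent therefore does not apply.
- A reader might infer that the 0–74 class contradicts Table 1. It does not. Table 1 governs the Per Protocol set, the subgroup models use ITT, which keeps every randomised patient, and Table 1 itself notes that the baseline score may differ from screening. What remains is an uninformative class.

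It is also fair to say that a merged class would stay thin: 3.9% to 24.9% of 174, or about 7 to 43 patients across three arms in the first set.

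**Conclusion.** The point holds as a minor one. Dropping the continuous baseline score widens intervals by about 2–8% at assumed correlations of 0.4–0.6 and costs about 1 to 4 points of interaction power at 0.3–0.5. The loss reaches about 7 points only at 0.7. It also leaves the result dependent on which outcome scale is modelled. The false-positive rate is essentially unaffected.

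The secondary point holds for interpretability only: estimates for the 0–74 class would usually be unavailable or rest on one or two patients.

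The class counts, R² and correlations rest on assumed distributions, since the SAP gives none of them. The primary analysis, which adjusts for baseline, is not affected.

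**What to change.** In SAP 5.4.2, delete the clause that exempts the baseline-severity model from adjustment and keep continuous baseline IBS-SSS as a covariate alongside the classes. This brings the model into line with the other subgroup models and makes the 3-month and change-score versions give the same contrasts.

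Merge the lowest two classes, giving below 175, 175–300 and above 300. All ITT patients stay in the model. Any patient with a baseline score below 75 can be counted in the report of ineligible participants that SAP 4.1 already requires, while still contributing to the merged class.

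The cost is one line of wording and no new data. A separate estimate for 0–74 is given up, but it would rarely be available. The merger should not be presented as a gain in power.

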### 5.4.3 Regression analysis

To identify risk factors involved in the persistence of gastrointestinal symptoms and deduct conceptual models of gastrointestinal symptom persistence, we will use longitudinal data from the control group (UC and IBS) and conduct linear multiple mixed regression analyses adjusted for the diagnostic group, while taking into account the number of predictors and sample size (estimated at baseline  $n=78$  with  $n=39$  for each UC and IBS).

Regression analyses will be conducted separately for IBS-SSS and PHQ-15 as outcome utilizing outcome data from 6 and 12 months' follow-up. Pre-specified predictors for both analyses are gender, age, IBS-SSS baseline score, depression (PHQ-9), anxiety (GAD-7), somatic symptom related cognitions, emotions and behaviours (SSD-12), expected symptom severity in 6 months (NRS) and fecal calprotectin.

To avoid bias, patients from the intervention groups will not be included in these analyses. To compare risk factors across UC and IBS and to identify disease-specific and generic factors for gastrointestinal symptom persistence over time, we will conduct exploratory linear multiple mixed models including all patients from the control group with disease as a factor. We will also compare the results of the disease-specific regression analysis for symptom persistence in UC versus IBS and conduct further exploratory analyses which include all randomized patients and timepoints in a comprehensive model to predict the course of IBS-SSS and PHQ-15. In order to account for unevenly spaced observations (i.e. 3 or 6 months) a spatial covariance structure will be used to model the longitudinal random effect.

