## 1.2 Objectives

Since both factors can potentially be modified by targeted interventions, this study will investigate defined mechanisms of action; namely, whether persistent gastrointestinal symptoms in UC and IBS can be influenced by modifying dysfunctional symptom expectations and illness-related anxiety. Studying a primarily inflammatory and a primarily functional bowel disease in parallel allows for the investigation of whether the same mechanisms of symptom persistence are involved for these two different, yet related diseases.

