### 5.4 Additional analyses

#### 5.4.1 Mediation analysis

In order to analyse whether effects on persistent gastrointestinal symptoms resulted through changes in dysfunctional symptom expectations or illness-related anxiety, we will conduct causal mediation analyses. Mediation analyses will test whether in patients receiving GUT EXPECT, changes in the mediating variables at the 6 weeks' assessment predict a reduction in gastrointestinal symptom severity (IBS-SSS) at 3 months (primary outcome), 6 and 12 months. That is to say, the adjusted total treatment effect (TE) will be divided into the indirect effect, which describes the treatment effect on persistent gastrointestinal symptoms via the mediators, and the direct effect, which describes the treatment effect not mediated through the mediators. Subsequently, the percentage mediated (PM) can be estimated. Only potential mediator-outcome confounders need to be controlled for due to randomisation and a possible treatment-mediator interaction must be considered. To account for mediator-outcome confounding, we adjust generally for gender and diagnosis.

In our main mediation analysis given in Figure 2, we include expectations of symptom severity (EXP 2) and illness-related anxiety (SSD-12) at 6 weeks FU as mediating variables. We use linear structural equation model to estimate the effect of the mediating variables on the IBS-SSS at 3 months and will repeat this analysis, when 6 and 12 month data is available.

The following sensitivity analyses are to be carried out to validate the results and investigate changes in the (in)direct effects and PM with regard to our main mediation model:

- additional adjusting for fecal calprotectin, IBS-SSS at baseline and duration of symptoms and, in a next step, for mediators at baseline (Figure 2)
- include an interaction between the treatment and the mediator(s)
- handling missing values by using the full information maximum likelihood (FIML) approach in the adjusted model with all confounders.

[figure not shown]

Figure 2: Main mediation analysis model

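### SAP 5.4.3 aims to separate disease-specific from generic risk factors but names no test of whether a predictor's slope differs between UC and IBS

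*SAP*

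**What the plan says.** Section 1.2 justifies studying the two diseases in parallel by the question "whether the same mechanisms of symptom persistence are involved for these two different, yet related diseases".

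For risk factors, section 5.4.3 takes this up in the control group: "To compare risk factors across UC and IBS and to identify disease-specific and generic factors for gastrointestinal symptom persistence over time". It names two routes:

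- Pooled model: "exploratory linear multiple mixed models including all patients from the control group with disease as a factor".
- Separate models: "We will also compare the results of the disease-specific regression analysis for symptom persistence in UC versus IBS".

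Eight predictors are pre-specified: gender, age, baseline IBS-SSS, PHQ-9, GAD-7, SSD-12, expected symptom severity and fecal calprotectin. They are used for two outcomes, IBS-SSS and PHQ-15, at 6 and 12 months. The control group is put at 78 at baseline, 39 per disease. No predictor-by-disease interaction is named, and no rule is given for comparing the separate regressions.

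Two other sections bear on the point. Section 5.4.2 tests the interaction of treatment group with diagnosis on the 3-month IBS-SSS, with diagnosis as a key subgroup. In the mediation analysis of section 5.4.1, diagnosis enters only as a covariate: "we adjust generally for gender and diagnosis".

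**The concern.** Whether a risk factor is disease-specific or generic is a question about slopes: is the association between predictor and outcome different in UC and in IBS? A disease main effect moves the intercept and leaves one shared slope per predictor, so it cannot answer that question.

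Setting two separate regressions side by side does not answer it either unless the difference between the coefficients is estimated with its uncertainty. If the comparison were made by asking which predictors reach significance in which disease, chance alone would often give different answers in two small samples with the same true slope. A generic factor could then be reported as disease-specific. What is at stake is the credibility of the risk-factor comparison across diseases. The primary result is not at stake.

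**Working it through.** **Control-group size.** Section 2.3 gives 29 per group and 25% loss: 29/0.75 = 38.7, so 39 per arm and disease, and 3 × 39 = 117 per disease. With 1:1:1 allocation, 117/3 = 39 controls per disease and 234/3 = 78 in all. The figures in section 5.4.3 reproduce. The 25% loss is stated only to 3 months. Carried forward to 6 and 12 months as an assumption, it leaves 39 × 0.75 ≈ 29 per disease. With eight predictors that is 39/8 = 4.9 or 29/8 = 3.6 patients per predictor.

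**What the pooled model can show.** Three places in the SAP bear on the word factor. Section 5.2.1 adds disease as a factor while assuming no interaction with treatment. Section 5.4.2 spells out an interaction when one is meant (group by subgroup variable), and section 5.4.1 does the same (treatment by mediator). On that usage, disease as a factor in section 5.4.3 is a main effect with one common slope per predictor.

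**What comparing by significance would do.** This rule is an assumption; the SAP gives none. Further assumptions are one follow-up outcome per patient, eight independent predictors, two-sided 5% (section 3.1), and the same true partial correlation r in both diseases.

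- Power for one slope: noncentral t with df = n − 9 and noncentrality r/√(1 − r²) × √(n − 9).
- Chance that exactly one disease is significant: 2p(1 − p), where p is that power.

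Example, r = 0.3: r/√(1 − r²) = 0.3145. At n = 39 the noncentrality is 0.3145 × √30 = 1.72, so p = 0.385 and 2 × 0.385 × 0.615 = 0.47. At n = 29 it is 0.3145 × √20 = 1.41, so p = 0.268 and 2 × 0.268 × 0.732 = 0.39.

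| Partial r in both diseases | Power, n=39 | Exactly one significant, n=39 | Power, n=29 | Exactly one significant, n=29 |
|---|---|---|---|---|
| 0 | 5% | 9.5% | 5% | 9.5% |
| 0.1 | 8% | 15% | 7% | 13% |
| 0.2 | 19% | 31% | 14% | 24% |
| 0.3 | 39% | 47% | 27% | 39% |
| 0.4 | 64% | 46% | 46% | 50% |
| 0.5 | 86% | 24% | 69% | 43% |
| 0.6 | 98% | 4% | 89% | 20% |

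A simulation (4,000 runs per setting, r from 0.1 to 0.5) agrees: for r = 0.3 it gives 48% at n = 39 and 40% at n = 29.

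**What an interaction test would do.** In the same simulated data, a direct test of the slope difference was falsely significant in 4.2% to 5.3% of runs. Its power is low. The noncentrality is [r1/√(1 − r1²) − r2/√(1 − r2²)] / √(2/(n − 9)), with df = 2(n − 9):

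- r 0.3 in one disease and 0 in the other: 0.3145/√(2/30) = 1.22 gives 22% at n = 39; 0.3145/√(2/20) = 0.99 gives 16% at n = 29.
- r 0.5 and 0: 60% at n = 39 and 43% at n = 29.

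These figures let all eight slopes differ by disease. Freeing one slope at a time leaves slightly more residual degrees of freedom (78 − 11 = 67 instead of 60 at n = 39), so they are approximate for that version. Eight independent unadjusted tests have a family-wise error of 1 − 0.95⁸ = 34% per outcome.

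**The case against.** The strongest reply is that the wording is unclear rather than the model wrong. Section 5.4.3 first describes control-group models adjusted for the diagnostic group, then a separate model with disease as a factor, introduced by the aim of finding disease-specific factors. If the second model held only a main effect, it would largely repeat the first, so interactions may have been intended. That is plausible, but the text does not say it, and the SAP names interactions elsewhere when it means them. The wording needs settling either way.

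A reader might infer that the UC-versus-IBS question is never tested. The document does not support that: section 5.4.2 tests treatment by diagnosis and reports subgroup means and pairwise differences with 95% CIs when p is below 0.15. That test covers the treatment effect. It does not cover the risk-factor slopes.

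A reader might also infer that false differences are likely. That holds only if results are compared by significance. Comparing coefficients and their intervals fits the text equally well, and even under the significance rule the rate runs from about 4% to 50% over the r values tabulated. The calculation also ignores the repeated 6- and 12-month data and puts all eight predictors in each disease-specific model, although section 5.4.3 says the number of predictors and the sample size will be taken into account. These limits stand.

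On mediation, section 5.4.1 asks whether effects run through the mediators and does not claim to compare diseases there. Adjusting for diagnosis does not contradict that aim.

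**Conclusion.** The point holds for the risk-factor comparison. As written, section 5.4.3 has an aim about slope differences and no test of them: one route shares the slopes, and the other gives no contrast or rule. The 24–47% (n = 39) and 24–50% (n = 29) rates are conditional. They assume comparison by significance, equal partial r of 0.2 to 0.5, eight independent predictors and one outcome per patient; n = 29 also assumes that the 3-month loss applies later. They show what an unspecified comparison could do and do not predict what the analysts will do.

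Severity is minor to moderate. The cross-disease models are labelled exploratory, and no primary or confirmatory conclusion depends on them. Nor does the better method bring much certainty: with 16–22% power for partial r 0.3 versus 0, most real differences of that size would be missed.

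**What to change.** In section 5.4.3:

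- In the pooled control-group mixed model, add predictor-by-disease interactions, one predictor at a time.
- Report the UC slope, the IBS slope and their difference with a 95% CI, and call a factor disease-specific only on that difference.
- Keep the separate UC and IBS regressions as description.
- State that the interaction tests are exploratory, unadjusted (about 34% family-wise over eight independent tests) and low in power, so a non-significant interaction does not establish a generic factor.

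Optionally, add to section 5.4.1 an exploratory mediation run with diagnosis as moderator, reporting the difference in indirect effects with a CI.

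The cost is a few sentences of SAP text and some extra models on data already planned. The slope differences will have wide intervals, which states openly what two separate coefficient tables would leave the reader to guess.
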